There will be two groups that participants can be assigned to if they choose to participate in the study. Each person will be randomly assigned to one of these groups. One group will provide information about PrEP and HIV prevention and referral to PrEP clinics in the community. The second group will be the same as the first group but will also provide access to a CHW who will assist them with getting to a PrEP clinic and also helping them with other needs they may have.

A member from the study team will review the informed consent documents with the prospective participants and ask them questions to make sure they are eligible to participate in this study (PrEP-LINK eligibility and demographic screening form). Their responses to the prescreen form will not be shared with anyone outside of the study and will not contain any identifying information. They will be kept completely private, and will be in a password protected, encrypted database on a secured server at UAMS that can only be accessed by designated study staff.

Before we collect this information, we ask that participants provide their name so that we can assign a 9-digit study-ID number to de-identify their responses. Names will be stored separately from responses in locked filing cabinet in a secured office and will never be connected. At the end of the study, the link between the name and the study ID will be permanently destroyed.

Random Assignment to Study Condition. Once qualified for the study, we will randomly assign them to one of the two study groups. Once assigned to a group, after the completion of the

Table 4: Points of Contact for each Assessment for Aims 2 and 3

Type of Visit	Assessment	Location
Eligibility Screen	Education and Screening for initial PrEP indication including HIV rapid testing or self-report of recent negative HIV test within correctional facility	Pulaski County Jail, Central Arkansas Community Corrections Center, East Central Arkansas Community Corrections Center, Hidden Creek Opportunity Center, Quality Living Center, Better Community Development, Inc.
Consent, Enrollment	Baseline Research Assessment	CED Core community site
Presentation at PrEP Program for PrEP prescription dispensed	Baseline Research Assessment	Community based PrEP Provider
PrEP intervention sessions	Adherence assessment (self-report only), sexual risk ACASI, post-incarceration issues and HIV risk only	Community based PrEP provider or CED Core Community site

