Title: Linking High-Risk Jail Detainees to HIV pre-exposure Prophylaxis: PrEP-LINK

PI: [name]

Site: University of Arkansas for Medical Sciences

Short-term follow up assessment	Full assessment battery, including adherence assessment (self-report and clinical chart abstraction)	CED Core community site
Long-term follow up assessment	Full assessment battery, including adherence assessment (self-report and clinical chart abstraction)	CED Core community site

baseline data collection measures the study research assistant will inform the community health worker and the participant to what group they were assigned to.

The participants will take place in the following activities over the course of 12 months:

- An HIV test using the FDA-approved OraQUICK ADVANCE® Rapid HIV Antibody Tests or self-report of recent (within 12 months) HIV test within correctional facility.
 - If HIV rapid testing is completed during eligibility screening visit, during the testing process the participant will receive:
 - (1) Pre-test counseling: A member of the research team, who has been trained by the Arkansas Department of Health to perform HIV counseling, will provide information on HIV and the meanings of a positive and negative test. Participants will have an opportunity to ask questions and will be offered prevention counseling.
 - (2) HIV testing: To test for HIV, a member of the research team will use the FDA approved OraQUICK ADVANCE® Rapid HIV Antibody Test.
 - (3) Post-test counseling: They will find out the results of their HIV test about 20 minutes after being tested. A member of the research team will go over the results of the test and engage in routine post-test counseling.
 - If tested positive for HIV, we will refer to the Arkansas Health Department for confirmatory testing and medical care. Study staff will also follow up to see if they received a confirmatory test. Additionally, any information collected up to that point will be destroyed and their participation in the study will be complete.
 - All participants will receive:
 - (4) PrEP counseling: Following screening and after the completion of the baseline assessment survey, participants will receive information about PrEP using materials developed by the Centers for Disease Control and Prevention (CDC). This includes a brochure that lists local clinics where PrEP is available and how to make an appointment.

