Trauma (Traumatic Life Events Checklist)	Based on Life Events Checklist by: Gray, M., Litz, B., Hsu, J., & Lombardo, T. (2004). Psychometric properties of the Life Events Checklist. Assessment , 11, 330-341. doi: 10.1177/1073191104269954v Weathers, F.W., Blake, D.D., Schnurr, P.P., Kaloupek, D.G., Marx, B.P., & Keane, T.M. (2013). The Life Events Checklist for DSM-5 (LEC-5). Instrument available from the National Center for PTSD at www.ptsd.va.gov	31-32	
Depression (Patient Health Questionnaire – 9 item version for Depression Symptoms)	Kroenke, K., Spitzer, R. L., & Williams, J. B. (2001). The Phq-9. Journal of general internal medicine , 16(9), 606-613.	33	
Discrimination (Major Experiences of Discrimination Scale)	Williams, D.R., Yu, Y., Jackson, J.S., & Anderson, N.B. (1997). Racial differences in physical and mental health: Socioeconomic status, stress, and discrimination. Journal of Health Psychology , 2(3), 335 -351	34-37	
Healthcare Access	National Health Interview Survey(CDC, 2018)	38-42	
Health and Utilization	RAND-36 Item Health Survey, ASI Lite, Medial Mistrust Survey, Commonwealth survey, survey on Disparities in quality of Health Care 2001	43-44	
Medical Mistrust	Medical Mistrust Index v2.2	45-47	
Social Support (Multidimensional Scale of Perceived Social Support)	Zimet, G.D., Dahlem, N.W., Zimet, S.G. & Farley, G.K. (1988). The Multidimensional Scale of Perceived Social Support. Journal of Personality Assessment , 52, 30-41.	48	
Civic Engagement	Compiled for this study by the PIs	49	

- HIPAA Authorization Form

Title: Linking High-Risk Jail Detainees to HIV pre-exposure Prophylaxis: PrEP-LINK

PI: [name]

Site: University of Arkansas for Medical Sciences

- This will be completed at baseline to allow the research team to collect medical records at the end of participation in the intervention regarding when participant first started taking PrEP medication and how often participant took PrEP medication.
- The following will be collected from the PrEP Clinic during participation in the study (12 months).
 - When participant first started taking PrEP medication for HIV prevention
 - How often participant took PrEP medication for HIV prevention
- Medical Records Release (HIPAA Release of Information to UAMS)

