exposure prophylaxis. If effective, the proposed intervention is likely to substantially improve adherence to PrEP and thereby increase the efficacy of the medication in preventing HIV seroconversion, particularly among individuals with criminal justice experience. Reduction in the incidence of HIV infection among individuals enrolled is also likely to lead to decreased transmission in the community as a whole. Study participants will be compensated for their participation. Some may feel empowered by being involved in research that may impact correctional and community health policy and practice and may enjoy the interaction with members of the study team.

Data Handling and Recordkeeping

Protecting Confidentiality: All members of the research team will treat participant data with the strictest attention to confidentiality. Data will be collected from participants in settings in the community and in correctional facilities in such a way that neither privacy nor confidentiality is compromised. All records and data will be safeguarded in accordance with the policies of the participating IRB. Questionnaires will not include participants' name or any other identifying information. Data for this phase of the study will be brief eligibility screens study (see Appendix PrEP-LINK eligibility and demographic screening form) and the baseline surveying tool (see Appendix PrEP-LINK Baseline Battery). Only members of the study team (PI [name], co-Is [name] and the study RAs, [name] and [name]) will have access to the data. At the conclusion of the study, the data will be stored electronically until analyses are completed. Electronic Data will be kept for the requisite 7 years, as per UAMS administrative guidelines.

Before we collect any information, we ask that participants provide their name so that we can assign a 9-digit study-ID number to de-identify their responses. Names will be stored separately from responses in locked filing cabinet in a secured office and will never be connected. At the end of the study, the link between the name and the study ID will be permanently destroyed. The participant ID link file will be kept separately in a password-protected folder/document on a secure UAMS server. All locator forms will be stored separately from the responses and destroyed at the completion of data collection.

Data Analysis

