Measures. The primary intervention measures, including common measure across both studies are provided above in the description of Aim 2. As part of Aim 3, data will be collected at all follow-up time points (3, 6 and 12 months) by the study RA. Additional measures are provided below.

Additional Secondary Measures for Aim 3

1) PrEP adherence. Self-reported PrEP adherence will supplement clinical chart abstraction. An assessment of the optimal period for self-reported antiretroviral adherence (using electronic monitoring data as the standard for predictive validity) found that longer time periods (e.g., 30 days versus 4 days) were more accurate for assessing adherence than shorter time periods.⁵¹ Therefore, we will use adherence over a 30-day period as self-reported adherence outcome.

Title: Linking High-Risk Jail Detainees to HIV pre-exposure Prophylaxis: PrEP-LINK

PI: [name]

Site: University of Arkansas for Medical Sciences

2) HIV risk behaviors/behavioral adjustment. Participants' HIV-transmission risk behaviors will be assessed with the TCU HIV/AIDS Risk Assessment, which is designed specifically for CJ-involved individuals,⁵² at all three data collection time points. We will collect more detailed data on sexual behaviors, including number of sexual partners, sexual activities, and condom use based on EXPLORE study measures. These measures are valid and reliable among high-risk men.⁵³

3) Substance use. Participants' alcohol use will be measured with the Alcohol Use Disorders Identification Test - Consumption (AUDIT-C) and the Addiction Severity Index - Lite (ASI-Lite), both of which have been validated for use with diverse populations (e.g., African American, Hispanic/Latino, and White).⁵⁶

Data analysis. Data analysis will focus on the feasibility, acceptability, and preliminary efficacy of the PrEP-LINK pilot intervention.

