The preliminary efficacy of the intervention will be determined by assessing the primary outcome of PrEP uptake by looking at the medical charts of the participants. A secondary outcome will be PrEP adherence defined by participants who were adherent to the medication determined by self-report at 3, 6, and 12 months. Following intent-to-treat (ITT) principles, all

Title: Linking High-Risk Jail Detainees to HIV pre-exposure Prophylaxis: PrEP-LINK

PI: [name]

Site: University of Arkansas for Medical Sciences

randomized participants will be included in data analyses. Standard bivariate analytic techniques, such as Spearman rank-order correlations, odds ratios, and Fisher's exact tests, will be used to assess preliminary associations between the intervention and each measure of PrEP uptake and to identify factors associated with the outcomes. Generalized linear regression models will be informed by these bivariate analyses.

In addition, we will test the randomization process by comparing the baseline demographic and confounding variables of the participants in each arm with Fisher's exact test for dichotomous variables, chi-square tests for nominal variables, *t*-tests for normally distributed continuous variables, and Wilcoxon signed-rank tests for non-normally distributed continuous variables, with statistical significance determined at alpha ≤ 0.05 . Any variable for which randomization does not result in equal proportions in each arm will be incorporated into the multiple-regression models as a potential confounding variable. Attrition effects will be evaluated by testing whether systematic differences exist between those participants who complete the research versus those who drop out. Thus, we can determine any potential bias introduced by attrition from the study.

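### The study RA role both discloses the arm and collects follow-up data, and no interviewer masking or chart abstractor is specified

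*Combined protocol and SAP*

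**What the plan says.** Five places bear on this point.

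- **Random Assignment to Study Condition** (the sentence continues after Table 4): once baseline measures are complete, "the study research assistant will inform the community health worker and the participant to what group they were assigned to".
- **Data Analysis, Measures**: for Aim 3, "data will be collected at all follow-up time points (3, 6 and 12 months) by the study RA".
- **Table 4**: the short- and long-term follow-up rows both read "Full assessment battery, including adherence assessment (self-report and clinical chart abstraction". ACASI appears once, in the row for PrEP intervention sessions: "Adherence assessment (self-report only), sexual risk ACASI, post-incarceration issues and HIV risk only".
- **HIPAA Authorization Form**: authorization is taken at baseline to "allow the research team to collect medical records at the end of participation in the intervention". The separate Medical Records Release is collected once the participant has chosen a provider, and the records then go to UAMS. Neither item says who abstracts the charts.
- **Data Handling and Recordkeeping**: access is limited to the PI, the co-investigators and two RAs ("the study RAs, [name] and [name]) will have access to the data"). Tasks are not divided between the RAs.

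On the outcomes, Data Analysis first describes "assessing the primary outcome of PrEP uptake by looking at the medical charts of the participants". The later paragraph on the primary analysis adds self-reported PrEP use to the charts. Adherence, a secondary outcome, is determined by self-report. The documents do not mention masking of interviewers, abstractors or analysts.

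**The concern.** A participant in this trial cannot be masked, but the person asking the questions can be. If the interviewer knows who had a CHW, that person may probe more in one arm, accept a vaguer account of PrEP use, or put more effort into finding a clinic chart. Each of these can create a difference in recorded uptake where none exists. PrEP uptake is a primary outcome, and the results are meant to inform a later multi-site trial, so a distorted estimate would carry forward.

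The exposure is not equal across outcomes. Self-reported use and adherence come from interviews of about an hour, which may be held by phone or video, so they depend most on the interviewer. A start date in a clinic record is fixed once the chart is found. The weak step there is finding it, since the release follows the participant's choice of provider. Intervention participants are expected to have CHW contact at least weekly and controls have none, so staff may learn of clinic visits more readily in one arm.

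**Working it through.** **Step 1. Roles, side by side.**

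| Task | Assigned to | Where |
|---|---|---|
| Tell participant and CHW the arm | study research assistant | Random Assignment to Study Condition |
| Aim 3 follow-up data | study RA | Data Analysis, Measures |
| Obtain clinic records | research team / UAMS | HIPAA Authorization Form; Medical Records Release |
| Abstract charts | not named; listed within follow-up assessments | Table 4 |
| Number of RAs | two, tasks not divided | Data Handling and Recordkeeping |

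Disclosure and follow-up collection fall to one role. Whether they fall to one individual is not stated.

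**Step 2. Inputs for an illustration.** The plan has no figure for assessor bias, so there is none to reproduce. Group sizes: 40 per arm (Power Calculations); 55 per arm (110 for Aim 3, equal split assumed, 110/2); 50 as a value in between. Two-sided alpha of 0.05, from Data Analysis. Assumed: the same true uptake in both arms (0.3 or 0.5), and over-recording of b = 0, 5 or 10 points in one arm only.

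As a check on the formulas, the plan's power statement (0.50 v 0.76, 40 per group, one-tailed 0.05, 80%) comes out at 78.6% with pooled variance and 80.4% with unpooled variance. It reproduces.

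**Step 3. One case by hand.** Take 40 per arm, true uptake 0.5, b = 0.10, so recorded uptake is 0.50 v 0.60.

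- Pooled standard error: sqrt(2 × 0.55 × 0.45 / 40) = 0.1112
- Unpooled standard error: sqrt((0.25 + 0.60 × 0.40) / 40) = 0.1107
- Upper tail: 1 − Φ((1.96 × 0.1112 − 0.10) / 0.1107) = 1 − Φ(1.066) = 0.143
- Lower tail: Φ((−1.96 × 0.1112 − 0.10) / 0.1107) = Φ(−2.873) = 0.002
- False-positive rate: 0.143 + 0.002 = 14.5%

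The same formula gives 7.3% for b = 0.05. With 55 per arm it gives 8.2% and 18.3%.

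**Step 4. Exact enumeration.** For every pair of counts, the binomial probabilities are multiplied and summed where the test rejects. Ranges run over 40, 50 and 55 per arm and true uptake of 0.3 and 0.5.

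| Over-recording in one arm | Pooled z test | Fisher's exact test |
|---|---|---|
| 0 points | 4.5-5.7% | 2.8-3.5% |
| 5 points | 7.4-9.0% | 4.6-5.9% |
| 10 points | 15.2-20.3% | 10.5-14.8% |

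**Step 5. Effect on the estimate.** Whatever the test, b points of over-recording in one arm move the estimated difference by b points. Against the 26-point difference in the power statement, 5 points is 5/26 = 19% and 10 points is 10/26 = 38%.

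**The case against.** The strongest reply is that the main uptake measure is a clinic-generated start date, that self-reported adherence is to be checked against charts and serum drug levels, and that this is a pilot whose stated emphasis is acceptability and feasibility. Enrolment and completion proportions do not depend on masking. Much of this stands. It explains why the exposure lies mainly in self-report and in chart finding, and why this is an inexpensive improvement and not a fatal flaw. It does not dispose of the point: self-reported use enters the primary analysis, adherence is defined by self-report, and two-tailed tests between arms are planned.

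The size is also open to challenge. The 5- and 10-point biases have no source in the documents. Fisher's exact test, which the plan names, is conservative here, so 5 points leaves its error rate near nominal. The plan also names GEE models, so neither test in the table is definitive.

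A reader might infer more than the documents support:

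- **That one individual does both tasks.** Two RAs are listed without a division of work. Only the shared role is established.
- **That charts will be abstracted by someone who knows the arm.** Table 4 points that way by placing abstraction within follow-up, but no abstractor is named.
- **That ACASI is already available for these outcomes.** It is listed only for sexual risk at intervention sessions. Using it for PrEP use and adherence would be a new procedure, and remote visits complicate it.
- **That separating the roles would remove the bias.** Participants know their arm, RAs help the CHW at recruitment sites, and satisfaction ratings can reveal the arm.

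**Conclusion.** The point holds in a limited form: one role is given both arm disclosure and Aim 3 follow-up collection, no masking is described, and no chart abstractor is named, although two RAs are available. Self-reported PrEP use and adherence are the most exposed, followed by the effort spent finding charts; recorded start dates are less so. The false-positive rates in the working are illustrative. They rest on equal true uptake of 0.3 or 0.5, 40 to 55 per arm, and an assumed bias confined to one arm. They show what bias of that size would do, not that it will occur. The change is worth making because it is cheap and the estimate will inform a larger trial.

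**What to change.** Amend Random Assignment to Study Condition and the Measures paragraph of Data Analysis as follows.

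1. One existing RA discloses the arm and liaises with the CHW.
2. The other RA, not told the arm, does the 6- and 12-month interviews and is named as chart abstractor.
3. Chart searches use one fixed clinic list and one set of chart queries for both arms.
4. Intervention satisfaction ratings are collected last, or by the RA who already knows the arm.
5. Each case where the assessor learns the arm is recorded and reported.

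Self-completion of the PrEP use and adherence items could be added. It is an optional extension and would need a workable format for phone and video visits.

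The cost is a short amendment, less flexible RA scheduling and some accidental unmasking. Items 1 to 5 need no new staff. Participants' own reporting bias will remain and should be acknowledged when results are reported.

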Primary outcomes will include acceptability and feasibility of the intervention, as well as PrEP uptake. Secondary outcomes will include adherence and retention in PrEP-related medical care at three, six and 12 months. Results will inform a subsequent multi-site RCT to test efficacy of the intervention in improving PrEP uptake, adherence, and retention in care among transitioning out of jail.

Between study aims 2 & 3 a total of 120 subjects will be consented with approximately 10 for aim 2 and 110 for aim 3.

NOTE: For this IRB application, we are only seeking approval for activities related to AIMs 2-3. AIM 1 was addressed in IRB #207297.

Study Design and Procedures

Human Subjects Involvement, Characteristics, and Design: Given the scope of inquiry and proposed project's aims, criminal justice (CJ) involved individuals are the human subjects of this project. Our research team understands that CJ-involved individuals represent a vulnerable population, as the correctional setting may be perceived as a coercive environment. Therefore, all research must be conducted with rigorous ethical standards and with numerous safeguards in place to protect participants. A 2006 Institute of Medicine report on research involving prisoners called for the following requirements:

- 1) a risk-benefit approach, whereby the potential benefits of the research to the prisoners outweigh the potential risks;
- 2) research should be conducted with "collaborative responsibility," referring to the idea that the design and implementation of the research should include the input of all relevant parties (including prisoners and correctional administrators);
- 3) voluntary informed consent must be obtained, and privacy maximized; and

Title: Linking High-Risk Jail Detainees to HIV pre-exposure Prophylaxis: PrEP-LINK

PI: [name]

Site: University of Arkansas for Medical Sciences

4) research must be monitored throughout the course of the study in order to verify compliance with approved protocols and to detect and report adverse events. The research plan described in this application complies with all of these requirements. Below each aim and the relevant human participants' involvement, characteristics and design are described.

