 - If they decide to initiate PrEP, they will be prescribed PrEP medications by a physician in accordance with routine clinical care at their local PrEP clinic in the community.

Title: Linking High-Risk Jail Detainees to HIV pre-exposure Prophylaxis: PrEP-LINK

PI: [name]

Site: University of Arkansas for Medical Sciences

Only participants who test negative for HIV on their rapid test will be eligible to participate in the study. Individuals in the jail with a preliminary positive HIV test result will be immediately referred to the jail medical division, operated by TurnKey, Inc. for confirmatory testing.

Individuals tested in the community will be immediately referred to the Arkansas Department of Health for confirmatory testing.

- A baseline assessment survey (SEE: PrEP-LINK Baseline Battery) to be used during all 3 data collection time points (baseline, 6-month and 12-month)
 - The baseline assessment survey will ask questions about education, job status, criminal justice history, substance use, sexual behaviors, and other behaviors which may put individuals at risk for HIV, in addition to questions on knowledge and interest in PrEP.
 - The baseline assessment survey includes the following measures and it to be used in both **Specific Aims 2 & 3**:

Measure Name	Citation	Baseline Battery Page Number	Notes
PrEP-LINK Cover Sheet	Compiled for this study by the PIs	1	For internal tracking purposes
Demographics	Compiled for this study by the PIs	2-5	
Criminal Justice Involvement History	Compiled for this study by the PIs	5-6	
Health Insurance	Compiled for this study by the PIs	6	
HIV Sex Risk Perception	Compiled for this study by the PIs	7	
Income (ASI Lite)	McLellan, A.T., Luborsky, L., O'Brien, C.P. & Woody, G.E. (1980). An improved diagnostic instrument for substance abuse patients: The Addiction Severity Index. Journal of Nervous & Mental Diseases , 168, 26-33	8-9	
PrEP Knowledge (PrEP Knowledge Scale, RADAR)	Parsons, J. T., Rendina, H. J., Lassiter, J. M., Whitfield, T. H., Starks, T. J., & Grov, C. (2017). Uptake of HIV pre-exposure prophylaxis (PrEP) in a national cohort of gay and bisexual men in the United States: the motivational PrEP cascade. Journal of acquired immune deficiency syndromes (1999), 74(3), 285.	10	

Title: Linking High-Risk Jail Detainees to HIV pre-exposure Prophylaxis: PrEP-LINK
 PI: [name]
 Site: University of Arkansas for Medical Sciences

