 - This will be collected at any time throughout the study once a participant has selected a specific PrEP provider, for medical records to be collected by UAMS for the duration of their participation in the intervention regarding PrEP initiation and adherence.

Follow-Up Assessments. Everyone will be asked to do follow-up assessments below:

3 Month Locator Check in:

After 3 months, a member of the study team will contact the participant to see how they are doing (PrEP-LINK Locator Form).

6 Month Assessment (Visit 2):

Participants will complete a survey that will take approximately one hour at a public location in Little Rock that is convenient for them (See: PrEP-LINK Baseline Battery). This may be UAMS, local PrEP clinic, a public library, or other private meeting room. This may also take place over the phone, Zoom, FaceTime, or other platform preferred by the participant to allow for social distancing during the Covid-19 pandemic.

9 Month Locator Check in:

After 9 months, a member of the study team will contact them to see how they are doing (PrEP-LINK Locator Form).

12 Month Assessment (Visit 3):

Participants will complete a survey that will take approximately one hour at a public location in Little Rock that is convenient for them (See: PrEP-LINK Baseline Battery). This may be UAMS, local PrEP clinic, a public library, or other private meeting room. This may also take place over the phone, Zoom, FaceTime, or other platform preferred by the participant to allow for social distancing during the Covid-19 pandemic.

Individuals who are eligible and willing to participate will be involved in the study for 12-months. All participants will complete 3 in-person interviews every 6 months and will receive \$40 for their initial visit and \$40 for the 6-month and 12-month follow up visits. Participants will also complete 2 brief phone check-ins between interviews, after which they will receive an additional \$10 during their next in-person visit. Participants completing each interview and check-in will receive

Title: Linking High-Risk Jail Detainees to HIV pre-exposure Prophylaxis: PrEP-LINK

PI: [name]

Site: University of Arkansas for Medical Sciences

\$140 for their time. During the first and last study visit, participants will need to complete a saliva/spit based HIV screening test.

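### Self-reported PrEP use and adherence are declared outcomes at month 3, but the procedures schedule only a locator call then, with no PrEP measure

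*Combined protocol and SAP*

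**What the plan says.** **Analysis text.** In Data Analysis, the preliminary-efficacy paragraph takes the primary outcome, PrEP uptake, from medical charts and adds a secondary outcome: "PrEP adherence defined by participants who were adherent to the medication determined by self-report at 3, 6, and 12 months". The primary-analysis paragraph then compares uptake from charts together with self-reported PrEP use at visits at 3, 6 and 12 months. The Measures paragraph says in general terms that the research assistant collects Aim 3 data at those three follow-up points, but names no month-3 instrument.

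**Procedures.** The baseline assessment survey, whose measure list includes PrEP Use (battery pages 12-14) and PrEP Adherence (pages 15-16), is "to be used during all 3 data collection time points (baseline, 6-month and 12-month"). Under Follow-Up Assessments, month 3 reads: "After 3 months, a member of the study team will contact the participant to see how they are doing (PrEP-LINK Locator Form"). Month 9 is described in nearly the same terms: "After 9 months, a member of the study team will contact them to see how they are doing (PrEP-LINK Locator Form"). Month 6, by contrast, is headed "6 Month Assessment (Visit 2") and month 12 is Visit 3; both are surveys of about an hour. Maintaining Contact gives the purpose of the 3- and 9-month check-ins as keeping contact details current, and sets assessment windows for months 6 and 12 only.

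**Table 4.** One row, for PrEP intervention sessions, lists "Adherence assessment (self-report only), sexual risk ACASI, post-incarceration issues and HIV risk only". The short-term and long-term follow-up rows each list "Full assessment battery, including adherence assessment (self-report and clinical chart abstraction"). None of these rows carries a month.

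**The concern.** An outcome time point needs a scheduled measurement. Here the analysis text counts on month-3 self-report for a secondary outcome and for part of the primary analysis, while the procedures that staff would follow do not collect it.

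Three things are at stake:

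- **Missing by design.** Month-3 self-report would be absent for everyone, and the generalized estimating equation models for self-report would run on two follow-up points.
- **Not recoverable.** Adherence not asked about at the time cannot be rebuilt from a later survey with a 30-day recall.
- **Risk of unequal collection.** If staff fill the gap informally, the arms do not have equal contact. The intervention arm is expected to hear from the community health worker at least weekly; the comparison arm is described as receiving information and referral. The documents do not say this would happen, but they do not provide a common source that would prevent it.

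**Working it through.** **1. The plan's own figure: the payment total.** Follow-Up Assessments pays $40 for each of three interviews and $10 for each of two phone check-ins, and states a total of $140.

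3 × 40 + 2 × 10 = 120 + 20 = 140.

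The total reproduces only if month 3 is paid as a check-in. No third follow-up survey is budgeted.

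**2. The two schedules side by side.**

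| Month | Self-report in Data Analysis | Procedures |
|---|---|---|
| 3 | Adherence and PrEP use | Locator check-in by phone |
| 6 | Adherence and PrEP use | Visit 2, full battery |
| 9 | None | Locator check-in by phone |
| 12 | Adherence and PrEP use | Visit 3, full battery |

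Declared self-report follow-up points: 3. Dated in the procedures: 2. The procedures treat months 3 and 9 alike; the analysis text uses only month 3.

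**3. Can the 6-month survey stand in for month 3?** Inputs: the 6-month assessment opens 30 days before its target date (Maintaining Contact), and self-reported adherence covers 30 days (Additional Secondary Measures for Aim 3). Taking a month as 365.25 / 12 = 30.44 days:

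- Month 3 = day 91.3; month 6 = day 182.6.
- Earliest 6-month survey: 182.6 − 30 = day 152.6, about month 5.
- Start of its recall: 152.6 − 30 = day 122.6, about month 4.
- Gap to month 3: 122.6 − 91.3 = 31.3 days.

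So even the earliest permitted survey misses month 3 by about a month. This applies to adherence only. The documents give no recall period for PrEP use, so the same argument is not made there.

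**4. Can Table 4 supply it?** The intervention-session row has no month, and the sessions are not shown to include the comparison arm. The short-term follow-up row calls for the full battery; reading it as month 3 would contradict the survey's stated dates. The table leaves the question open.

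**5. Power.** The Power Calculations paragraph uses 40 per group, one-tailed alpha 0.05, and 0.50 against 0.76. With a pooled proportion of 0.63, the standard error is √(2 × 0.63 × 0.37 / 40) = 0.1080 under the null and √((0.25 + 0.1824) / 40) = 0.1040 under the alternative. Then z = (0.26 − 1.645 × 0.1080) / 0.1040 = 0.79, so power is about 0.79, close to the stated 80%. No input depends on a month-3 survey.

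**The case against.** The best reply is that much of what the plan wants at month 3 does not need a survey. The preliminary-efficacy paragraph takes uptake from charts, clinic records are to be collected over the 12 months and include start date and how often PrEP was taken, and self-report is described as a supplement to chart abstraction. This stands, and it limits the point to self-report. It does not remove it, because the secondary adherence outcome is explicitly defined by self-report and the primary analysis names self-reported use at month 3.

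Two stronger readings are tempting, and the documents do not support them.

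- **That the outcome statement in Specific Aims also conflicts.** It reads "Secondary outcomes will include adherence and retention in PrEP-related medical care at three, six and 12 months". It does not specify self-report, so clinic records could meet it at month 3.
- **That the feasibility criterion is contradictory.** Data Analysis counts participants assessed at baseline, 3, 6 and 12 months. A reader might infer that a locator call cannot qualify. Yet Follow-Up Assessments introduces its list, with the 3-month check-in first, as assessments asked of everyone. Maintaining Contact uses the word more narrowly and the feasibility text omits month 9, so the usage is loose, but it is not a contradiction.

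It can also be said that the Locator Form might ask about PrEP. The form is not in the documents, nothing says that it does, and its stated purpose is different.

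**Conclusion.** The inconsistency is real and confined to self-report at month 3. The preliminary-efficacy and primary-analysis paragraphs, and in general terms the Measures paragraph, require it; the survey schedule, the follow-up procedures and the assessment windows do not provide for it. One of three declared self-report follow-up points is affected.

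A reader might infer that the primary outcome as a whole is compromised. It is not: chart-based uptake and time-to-uptake, chart-abstracted adherence, retention in care, self-report at 6 and 12 months, and the power figure all stand.

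The conclusion assumes that staff follow the procedures as written and that the Locator Form carries no PrEP questions. The recall argument assumes the 30-day adherence definition and covers adherence only. For a pilot this is a modest item, but it should be fixed, because month-3 adherence that is not collected on time is lost.

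**What to change.** Reconcile the Measures, preliminary-efficacy and primary-analysis paragraphs with the survey schedule, Follow-Up Assessments and Maintaining Contact. Put months on the Table 4 rows, and have the feasibility text state what counts as assessed at month 3. Then choose one of the following.

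- **A. Collect it.** Add short questions on PrEP use and on adherence over 30 days, as defined under Additional Secondary Measures for Aim 3, to the existing 3-month call. Ask them identically in both arms, within a stated window, and say in Measures which items are collected at month 3. If the window is meant to keep the call clear of the 6-month adherence recall, 30 days after month 3 is too tight. On average months the call could fall on day 91.3 + 30 = 121.3, against a recall start of day 122.6, a margin of 1.3 days. For enrolment on 1 November in a non-leap year, the latest call would be 3 March and the earliest recall start 2 March, an overlap of a day.
- **B. Drop it.** Remove month 3 from the self-report outcomes in the Measures, preliminary-efficacy and primary-analysis paragraphs only. Keep 3-month uptake, retention in care and chart-abstracted adherence, and leave the Specific Aims statement as it is.

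**Cost.** Either option needs an IRB amendment, since Ethical Considerations requires approval of any amendment. A also makes a call that is already scheduled and paid somewhat longer. B otherwise changes wording only and accepts two self-report follow-up points.
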